##### Cycles 25 and beyond

Agent	Dose Level	Route	Day		Cycles
Lenalidomide	25 mg	PO	1-21	Repeat every 28 days x 3 for each cycle	Cycles 25 and beyond
Dexamethasone	40 mg*	PO	1, 8, 15, 22		

Cycle length = 84 days

\*Starting dose level of dexamethasone for patients  $\geq 75$  years old will be 20mg

Treatment schedule will follow the study schema outlined above. All patients will start with ibrutinib at the dose level determined by the phase I portion and dexamethasone 40 mg PO weekly. Lenalidomide 25 mg PO Days 1-21 will be added Cycle 2.

Treatment will be continued until disease progression as long as the patient continues to respond and does not have any unacceptable toxicity. All the patients enrolled in the trial will have a follow up for at least 3 years after registration to capture the secondary endpoints of the study.

7.2 Treatment by a local medical doctor (LMD) is not allowed.

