**EXCEPTIONS:**

- Adequately treated basal cell or squamous cell skin cancer
- Any *in situ* cancer
- Adequately treated Stage I or II cancer from which the patient is currently in complete remission, or
- Any other cancer from which the patient has been disease-free for  $\geq$ at least three years prior to registration

3.25 Concurrent therapy considered to be investigational.

**NOTE:** Patients must not be planning to receive any radiation therapy (except localized radiation for palliative care that must be completed prior to starting Cycle 1, Day 1).

3.26 Any of the following because this study involves an investigational agent whose genotoxic, mutagenic and teratogenic effects on the developing fetus and newborn are unknown:

- Pregnant women
- Nursing women (lactating females are eligible provided that they agree not to breast feed while taking lenalidomide)
- Men or women of childbearing potential who are unwilling to employ adequate contraception

3.27 Requires treatment with a strong cytochrome (CYP) 3A4/5 inhibitor (as outlined in Appendix X).

3.28 Major surgery  $\leq$ 4 weeks prior to registration.

3.29a History of stroke/intracranial hemorrhage  $\leq$ 6 months prior to registration.

3.29b Requires use of therapeutic anticoagulation prior to registration  
**NOTE:** thromboprophylaxis with any agent is permitted.

3.29c History of clinically significant bleeding or known platelet or coagulation disorder.

3.29d Clinically significant cardiac illness including New York Heart Association (NYHA) Class III or Class IV heart failure (Appendix VI), unstable angina pectoris, myocardial infarction within the past 6 months, or  $\geq$ Grade 3 cardiac arrhythmias noted  $\leq$ 14 days prior to registration.

3.29e Hepatic impairment

3.29e1 Phase I  
Any currently active, clinically significant hepatic impairment (Child-Pugh class A, B, or C according to the Child Pugh classification see Appendix XII).

3.29e2 Phase II  
Currently active, clinically significant hepatic impairment Child-Pugh class B or C according to the Child Pugh classification (see Appendix XII).

3.29f Known HIV+ patients  
EXCEPTION: If they meet the following additional criteria  $\leq$ 28 days prior to registration:

- CD4 cells  $\geq$ 500/mm^3
- Viral load of <50 copies HIV mRNA/mm^3 if on cART or <10,000 copies HIV mRNA if not on cART
- No zidovudine or stavudine as part of cART

3.29g Known Hepatitis B or Hepatitis C infection  

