#### 7.12 Phase II Treatment Schedule (To be implemented after FDA review of Phase I)

##### Cycles 1-24

Agent	Dose Level	Route	Day	Cycles
Ibrutinib	As determined in Phase I	PO	1-28	Cycle 1 and beyond
Lenalidomide	25 mg	PO	1-21	Cycle 2 and beyond (Not given in Cycle 1)
Dexamethasone	40 mg*	PO	1, 8, 15, 22	Cycle 1 and beyond

Cycle length = 28 days

\*Starting dose level of dexamethasone for patients  $\geq 75$  years old will be 20mg

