### **8.51 Dose Modification for Hepatic Impaired Subjects**

Ibrutinib is metabolized in the liver and therefore subjects with clinically significant hepatic impairment at the time of screening (Child- Pugh class B or C) are excluded from study participation. For subjects who develop mild liver impairment while on study (Child-Pugh class A), the recommended dose reduction for ibrutinib is to a level of 280 mg daily (two capsules). For subjects who develop moderate liver impairment while on study (Child-Pugh class B), the recommended dose reduction is to a level of 140 mg daily (one capsule). Subjects who develop severe hepatic impairment (Child-Pugh class C) must omit ibrutinib until resolved to moderate impairment (Child-Pugh class B) or better. Monitor subjects for signs of toxicity and follow dose modification guidance as needed (Refer to [Appendix XII](#)).

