d) Elimination – The excretion of ibrutinib is predominantly via the feces with approximately 80% recovered mostly within 2 days, whereas ~8% is excreted in urine. Approximately 1% of the ibrutinib is recovered as unchanged drug, all in feces. The half-life elimination is 4-6 hours. Overall, these PK characteristics resulted in minimal accumulation of both parent compound and metabolite PCI-45227 on repeated daily dosing of ibrutinib.

e) Special populations: a small increase in bioavailability was estimated with increasing age. Exposure is predicted to increase approximately 14% and decrease approximately 20% in subjects of 81 and 49 years of age, compared to a typical 67-year old subject. No statistically significant

effects were observed for the other covariates tested, i.e., sex, race, mild and moderate renal impairment, mild hepatic impairment and B-cell histology. The recommended doses for patients with mild and moderate liver impairment are 280 mg/day and 140 mg/day (Child-Pugh Class A and B, respectively). It is not recommended to administer ibrutinib to subjects with severe hepatic impairment (Child-Pugh Class C). Pediatric studies are still ongoing.

**15.16 Potential Drug Interactions:** Ibrutinib is primarily metabolized by cytochrome P450 enzyme 3A4/5. Voriconazole and posaconazole can be used concomitantly with ibrutinib as per the dosing guidance described in the specific clinical study protocol. All other strong inhibitors of CYP3A (eg, ketoconazole, indinavir, nelfinavir, ritonavir, saquinavir, clarithromycin, telithromycin, itraconazole, nefazodone, and cobicistat) should be avoided, and an alternative with less CYP3A inhibitory potential should be considered. If the benefit outweighs the risk and a strong CYP3A inhibitor must be used, see the recommended dose modifications described in the specific clinical study protocol.

If a moderate CYP3A inhibitor (eg, fluconazole, erythromycin, amprenavir, aprepitant, atazanavir, ciprofloxacin, crizotinib, diltiazem, fosamprenavir, imatinib, verapamil, amiodarone, dronedarone) is indicated in patients with B-cell malignancies, reduce the ibrutinib dose to 280 mg for the duration of the inhibitor use or as per recommended dose modifications described in the specific clinical study protocol. No ibrutinib dose modifications for moderate inhibitors are required in patients with cGVHD dosed with ibrutinib 420 mg.

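### Phase II starts patients with clinically significant Child-Pugh class A impairment at the phase I ibrutinib dose, although the protocol itself recommends 280 mg/day for them

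*Combined protocol and SAP*

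**What the plan says.** Four parts of the protocol bear on this.

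- **Eligibility.** Phase I (3.29e1) excludes "Any currently active, clinically significant hepatic impairment (Child-Pugh class A, B, or C according to the Child Pugh classification". Phase II (3.29e2) excludes only "Currently active, clinically significant hepatic impairment Child-Pugh class B or C according to the Child Pugh classification".
- **Starting dose.** The Phase II table in 7.12 gives the ibrutinib dose as "As determined in Phase I", and the text below it reads "All patients will start with ibrutinib at the dose level determined by the phase I portion and dexamethasone 40 mg PO weekly". The only exception visible in 7.12 is dexamethasone 20 mg from age 75.
- **Dose modification.** 8.51 sets a reduced dose of 280 mg daily, but only for those "who develop mild liver impairment while on study (Child-Pugh class A), the recommended dose reduction for ibrutinib is to a level of" that amount. It names class B and C as excluded at screening and gives no dose for class A present at screening.
- **Drug information.** 15.15e states: "The recommended doses for patients with mild and moderate liver impairment are 280 mg/day and 140 mg/day", for classes A and B respectively. In the same item, the covariate analysis looked for statistically significant effects and reports that no such "effects were observed for the other covariates tested, i.e., sex, race, mild and moderate renal impairment, mild hepatic impairment".

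**The concern.** The same liver state is dosed differently according to when it appears: 280 mg if it arises on study, the phase I dose if it is already there at registration. The protocol gives no clinical reason for the difference.

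Patient safety is at stake. 8.51 rests its rule on ibrutinib being metabolized in the liver. Phase I, which sets the dose carried forward, shuts out clinically significant class A impairment, so that dose will not have been tested in this group within the trial.

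There is also a practical conflict. An investigator who follows 15.15e and starts at 280 mg departs from 7.12 in Cycle 1, the cycle on which 13.7 judges major violations. The plan does not say how such a patient would be classified.

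**Working it through.** The plan states no figure to reproduce here. The check is a cross-reading plus dose ratios.

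**1. Can such a patient enter Phase II?** Yes, under 3.29e2. The laboratory limits in 3.17 (bilirubin at most 1.5 x ULN unless Gilbert's, AST/ALT at most 3 x ULN, PT/INR at most 1.5 x ULN) narrow the group but do not close it. Appendix XII also scores albumin, ascites and encephalopathy, and 3.17 limits none of these. For example, albumin of 2.8-3.5 g/dL (2 points) with one point on each of the other four measures gives 2 + 4 x 1 = 6, which is class A. Known hepatitis B or C is also admissible below the viral-load limit in 3.29g.

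**2. Does another rule set the starting dose?** None that is visible.
- 8.51 is worded for impairment that develops on study.
- The notes to 8.5 confine dose changes to adverse events attributed to study treatment, which baseline impairment is not.
- 15.19b reduces ibrutinib for CYP3A inhibitors, not for liver function.

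**3. How far apart are the two doses?** The phase I result is not in the documents, so the range is taken over the planned levels in 7.31. Ratio = phase I dose / 280 mg.

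| Dose level | Ibrutinib | Ratio to 280 mg |
|---|---|---|
| -1 | 280 mg | 280/280 = 1.0 |
| 1 (starting level) | 420 mg | 420/280 = 1.5 |
| 2 | 560 mg | 560/280 = 2.0 |
| 3 | 700 mg | 700/280 = 2.5 |
| 4 | 840 mg | 840/280 = 3.0 |

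Only level -1, the de-escalation level, removes the conflict.

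**4. What happens below 280 mg?** In 8.223 the first reduction from a 280 mg start is discontinuation. 8.51 allows 140 mg when class B impairment develops. A class A patient started at 280 mg would fall under both rules, so the next step has to be stated.

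**5. Who is meant by class A?** The lowest possible Child-Pugh score is 5 measures x 1 point = 5, and 5-6 points is class A. A patient who scores one point on everything is therefore class A by score. Any new rule must keep the qualifier that the impairment is clinically significant, or it would cut the dose of patients with normal livers.

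**The case against.** The strongest reply is that the protocol does give the dose. Section 15 is part of the protocol, 15.15e does not limit its recommendation to impairment acquired on study, and 8.51 gives the same 280 mg. On this view only a cross-reference is missing, and a careful investigator would apply 8.51 by analogy. Further, 7.12 defers to a schema whose Phase II figure is not shown; 8.51 attaches clinical significance at screening to classes B and C; Phase II opens only after FDA review of Phase I; and the covariate result in 15.15e is null for mild impairment.

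Part of this stands. The group is probably small, harm is not demonstrated, and a note in the schema cannot be ruled out. But 7.12 is the operative starting instruction and it addresses all patients; a recommendation within the pharmacokinetic information does not amend it. 3.29e1 does treat class A impairment as something that can be clinically significant. The item with the null covariate result still recommends 280 mg. FDA review comes before exposure but does not change the wording.

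Three stronger readings are tempting and are not supported:

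- A reader might infer that Phase I contains no class A patients at all. The exclusion reaches only currently active, clinically significant impairment; a normal score of 5 is class A.
- A reader might infer that Phase II lacks renal protection too, since 7.12 says "Lenalidomide 25 mg PO Days 1-21 will be added Cycle 2" without the renal exception found in 7.11. Section 8.31 and the footnote to Table 8.32 already carry the lenalidomide adjustment into Phase II.
- A reader might take the ratios as multiples of exposure or toxicity. They are ratios of prescribed dose only.

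**Conclusion.** The point holds as an internal conflict over a starting dose and should be fixed. As written, an eligible Phase II patient with clinically significant class A impairment at registration starts at 1.5 to 3 times the protocol's own recommendation, unless Phase I ends at 280 mg.

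This rests on two assumptions: that the unseen Phase II schema holds no hepatic exception, and that the phase I dose is one of the planned levels above 280 mg. The documents do not allow an estimate of how many patients are affected or of any added toxicity. The Phase II decision rule, sample size and error rates are not touched.

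**What to change.** Make three wording changes.

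1. Add to 7.12: *EXCEPTION: patients with clinically significant Child-Pugh class A hepatic impairment at registration start ibrutinib at 280 mg daily (see 8.51).*
2. Reword 8.51 so that its class A rule covers patients who *have at registration or develop on study* such impairment.
3. State the next step below 280 mg for these patients, settling whether 8.223 (discontinue) or the 140 mg level in 8.51 governs, and when.

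Keep the qualifier *clinically significant* throughout.

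The cost is protocol wording only. Bilirubin, albumin and INR are already measured within 14 days before registration (4.1, footnotes e and f), so no new test is needed for those components. Excluding class A as in Phase I would also remove the conflict, but that is an eligibility trade-off for the study team and is not needed to resolve the point.

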7.3 Phase I – determination of Maximum Tolerated Dose (MTD)

7.31 Dose Escalation (Phase I):

Dose level escalations/de-escalations will be done during the Phase I portion for Ibrutinib. In case any dose modifications to ibrutinib and/or dexamethasone are required during the Phase I portion due to specific adverse events requiring dose modifications (as outlined in Section 8 below), a specific discussion should be done with the study PI and appropriately documented. A patient on the Phase I portion of the study who develops a DLT should have treatment omitted until the toxicity resolves to Grade 1 or better or baseline, and then may be restarted at the next lower dose level for the DLT portion only. .

Only DLTs occurring in the first cycle and at the patient's first Dose Level of treatment will be used to guide dose determination for the Phase II portion of the trial per Section 16.22.

Dose level	Ibrutinib	Lenalidomide	Dexamethasone**
-1	280 mg	25 mg	40 mg
1*	420 mg	25 mg	40 mg
2	560 mg	25 mg	40 mg
3	700 mg	25 mg	40 mg
4	840 mg	25 mg	40 mg

\*Starting dose level

\*\*Starting dose level of dexamethasone for patients  $\geq 75$  years old will be 20mg

7.311 Three patients will be treated at each dose level and observed for a minimum of 28 days, to assess toxicities, before new patients are treated. Doses will not be escalated in any individual patient.

7.312 Investigators are to contact the Study Chair as soon as any dose-limiting toxicity (DLT) occurs.

7.32 **Definitions of DLT:** For this protocol, dose-limiting toxicity (DLT) will be defined as an adverse event attributed (definitely, probably, or possibly) in the first cycle to the study treatment and meeting the following criteria (as per CTCAE V4.0):

- Any Grade 3 or greater non-hematological toxicity will be a DLT, with the exception of: fatigue, inadequately treated nausea, vomiting, or diarrhea; inadequately treated hyperglycemia; or hypersensitivity reaction. A rash considered associated with immune activation phenomenon secondary to

lenalidomide and/or ibrutinib will not be considered a DLT and may be treated concurrent to study treatment with solumedrol (Recommended treatment would be with a Medrol Dose Pak®) For a baseline abnormality prior to drug therapy, a worsening by at least 2 CTCAE grades and of clinical significance will be considered a DLT.

- b) Grade 3 nausea, vomiting or diarrhea will be a DLT if it occurs despite appropriate maximal anti-emetic and/or antidiarrheal therapy.
- c) Grade 3 hyperglycemia will be a DLT if the patient is symptomatic or glucose level is  $>300$  mg/ml despite appropriate administration of insulin and/or oral antidiabetic agents.
- d) Grade 4 neutrophil count decreased lasting  $>7$  days or Grade 3 or 4 febrile neutropenia associated with fever ( $\geq 38.5^{\circ}\text{C}$ ).
- e) Grade 4 platelet count decreased. Grade 3 platelet count decreased lasting  $>7$  days or associated with Grade 2 or higher hemorrhage.
- f) Delay of treatment with ANY agent for  $\geq 14$  days due to possibly, probably or definitely treatment-related toxicity during Cycle 1.

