### 8.0 Dosage Modification Based on Adverse Events

Strictly follow the modifications in this table for the first cycle of combination treatment with ibrutinib, lenalidomide and dexamethasone, until individual treatment tolerance can be ascertained (**not including the treatment period where MTD of the combination is being determined as per Section 7.31**). Thereafter, these modifications should be regarded as guidelines to produce mild-to-moderate, but not debilitating, side effects. Reductions apply to treatment given in the preceding cycle and are based on adverse events observed since the prior dose.

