**ALERT:** **ADR reporting may be required for some adverse events (See Section 10)**

#### 8.1 General Considerations:

- a) Missed doses are to be omitted rather than made up, unless the dose of one of the study drugs was forgotten and remembered on the same day, in which case the dose can be taken that day. Any doses missed on a particular day are not to be made up the next day.

Doses that are considered to be vomited are not to be made up and a mention about the time of dose and time of vomiting episode should be made in the pill diary.

- b) If multiple toxicities are experienced, dose modifications will be based on the toxicity requiring the largest dose reduction.
- c) Reductions are based on the dose given in the preceding cycle and are based on toxicities with an attribution of possible, probable, or definite that were observed since the prior toxicity evaluation.
- d) If either ibrutinib or lenalidomide must be permanently discontinued, the patient will be removed from the protocol therapy.
- e) If a drug is omitted due to specific adverse events and the patient is on combination therapy, the other agents, considered unrelated to the adverse event may be continued.
- f) A dose omission of >28 days for ibrutinib or lenalidomide is not allowed. If a patient cannot be administered a dose for >28 days due to adverse events or any other reason, the patient should be removed from the study treatment and go to event monitoring.
- g) Patients will be removed from the study if we are unable to manage the adverse events they experience, and it is therefore necessary to permanently discontinue ibrutinib or lenalidomide. These events are listed in the tables in Section 8.3 and 8.5.

8.2 Dose Reductions for Phase I cycles 2 and beyond and Phase II portion (based on Adverse Events in Tables below):

8.21 The following recommended dose modifications will be utilized for ibrutinib, lenalidomide and/or dexamethasone separately as per the best judgment of which drug was most likely to have caused the toxicity:

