Psychiatric disorders	Confusion or Mood alteration ≥ Grade 2 (Severe disorientation; limiting selfcare ADL)		
Omit dexamethasone until symptoms resolve Restart with one dose level reduction If symptoms persist despite above measures, discontinue dexamethasone and do not resume Ibrutinib and lenalidomide should be continued.

CTCAE System/Organ/Class (SOC)	ADVERSE EVENT	AGENT	ACTION**
Other	Non-hematologic AE assessed as lenalidomide related ≥Grade 3		Omit dose and follow at least weekly If the AE resolves to ≤Grade 2, implement one dose reduction step and continue therapy

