16.223 If DLT is seen in 1 of 3 patients treated at a given dose level, up to 3 additional patients will be enrolled and treated at the same dose level. If DLT is seen in at least one of these additional three patients ( $\geq 2$  of 6), the MTD will have been exceeded and further accrual will cease to

this cohort. If dose-limiting toxicity (DLT) is not seen in any of the three additional patients, 3 new patients will be accrued and treated at the next higher dose level.

16.224 After enrolling 6 patients on a specific dose level, if DLT is observed in at least 2 of 6 patients, then the MTD will have been exceeded and defined as the previous dose unless only 3 patients were treated at the lower dose level. In that case, 3 additional patients will be treated at this lower dose level such that a total of 6 patients are treated at the MTD to more fully assess the toxicities associated with the MTD.

16.225 Dose de-escalation: If dose-limiting toxicity meets the stopping boundaries set by the above dose escalation algorithm at dose level 1 (for example, more than 1 out of 3 patients or more than 1 out of 6 patients), the next cohort of three patients will be entered at a dose level of -1. Further dose re-escalation will depend on the toxicity profile observed at these dose levels, and re-evaluation of the regimen by the study team may be done.

16.226 If a patient fails to complete the first cycle of treatment for reasons other than toxicity, the patient will be regarded as inevaluable and will be replaced.

16.227 Operating Characteristics for standard cohort of 3 design: The following table gives the probability of dose escalation at a single dose level as a function of the true probability of DLT at that level using the cohorts of 3 design described above.

True Rate of DLT (%)	Probability of Dose Escalation
10	0.91
20	0.71
30	0.49
40	0.31
50	0.17

16.23 Analysis Plans: All the relevant results pertaining to toxicity, MTD, response, timed endpoints and laboratory correlates will be examined in an exploratory and hypothesis-generating fashion. The small sample size and the heterogeneous patient population associated with phase I studies restricts the generalizability of the results. Any notable statistical result should only be viewed as preliminary evidence for further study in Phase II trials rather than a definitive finding in and of itself.

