#### 16.5 Data and Safety Monitoring:

16.51 The principal investigator(s) and the study statistician will review the study at least twice a year to identify accrual, adverse event, and any endpoint problems that might be developing. The Mayo Clinic Cancer Center (MCCC) Data Safety Monitoring Board (DSMB) is responsible for reviewing accrual and safety data

for this trial at least twice a year, based on reports provided by the MCCC Statistical Office.

16.52 Adverse Event Stopping Rules:

The stopping rules specified below are based on the knowledge available at study development. We note that the Adverse Event Stopping Rule may be adjusted in the event of either (1) the study re-opening to accrual or (2) at any time during the conduct of the trial and in consideration of newly acquired information regarding the adverse event profile of the treatment(s) under investigation. The study team may choose to suspend accrual because of unexpected adverse event profiles that have not crossed the specified rule below.

Phase I: By the nature of the “cohorts of three” phase I study design, toxicity (i.e., adverse events that are possibly, probably or definitely related to study treatment) stopping rules are in place for each dose level. Specifically, if 2 or more dose-limiting toxicities (DLTs) are observed during Cycle 1 at any given dose level, accrual to that dose level will be stopped, and patients will be accrued to the next lower dose level until a maximum of 6 patients are treated at the lower level. Note that a DLT that affects dose escalation is only that which is observed in the first cycle of treatment. However, adverse events for all cycles will be reviewed and the study team will determine whether the dose level needs to be adjusted for future patients. Specifically, if one of the following occurs, then enrollment should stop and the trial should be re-evaluated whether to continue or close the trial permanently to accrual. The study team will evaluate all toxicities on all dose levels before determining how to proceed.

- if  $\geq 1$  in the first 3 patients experience a Grade 4 or higher non-hematologic adverse event at least possibly related to treatment over all cycles at any dose level
- $\geq 2$  in the first 6 patients experience a Grade 4 or higher non-hematologic adverse event at least possibly related to treatment over all cycles at any dose level

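### A patient's first Cycle 1 DLT after an ibrutinib reduction goes uncounted under Section 7.31 but counts under the wording of Section 16.22, so the MTD can be biased upward

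*Combined protocol and SAP*

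**What the plan says.** - **7.31, counting rule.** Two conditions apply: "Only DLTs occurring in the first cycle and at the patient's first Dose Level of treatment will be used to guide dose determination". The sentence points to 16.22 as the algorithm it feeds. The sentence just before it concerns a patient who has already had a DLT and who "may be restarted at the next lower dose level for the DLT portion only".
- **7.31, other modifications.** It also foresees changes that need not follow a DLT: "In case any dose modifications to ibrutinib and/or dexamethasone are required during the Phase I portion due to specific adverse events requiring dose modifications". It refers to Section 8 for these and asks for a documented discussion with the study PI. It names no cycle.
- **16.52.** The Note reads: "Note that a DLT that affects dose escalation is only that which is observed in the first cycle of treatment". The stopping sentence before it speaks of two or more DLTs in Cycle 1 at a given dose level.
- **16.221 to 16.224.** These count patients with a DLT among the 3 or 6 treated at a level. They do not mention the patient's first dose level.
- **16.226 (and 13.5).** "If a patient fails to complete the first cycle of treatment for reasons other than toxicity, the patient will be regarded as inevaluable", and is replaced. Neither section mentions a patient whose dose was lowered in Cycle 1.
- **8.0 and 8.2.** 8.0 asks for strict use of its modifications in the first cycle of combination treatment, "not including the treatment period where MTD of the combination is being determined as per Section 7.31". 8.2 is headed "Dose Reductions for Phase I cycles 2 and beyond and Phase II portion (based on Adverse Events in Tables below".
- **8.51 and 15.19b.** These lower ibrutinib for liver impairment that develops on study and for a concomitant CYP3A inhibitor. Neither states a cycle limit.

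**The concern.** Section 7.32 already confines a DLT to the first cycle. The first-level condition is therefore the only part of the 7.31 sentence that removes an event which otherwise meets the DLT definition.

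After a DLT-driven reduction the condition does no harm, because the patient has already been counted. The difficulty is a patient whose ibrutinib is lowered in Cycle 1 without a prior DLT and who then has a first one. Read literally, 7.31 leaves that event out of the escalation decision. The patient is not replaced either: one who completes Cycle 1 is outside 16.226, and so is one who stops because of toxicity. The patient remains among the 3 or 6 with no counted DLT. Where the reduction lowered exposure, a DLT on less drug is evidence against the assigned level, so leaving it out works in the wrong direction.

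The MTD is the Phase I primary endpoint and sets the ibrutinib dose for Phase II (7.12). The count behind it should not depend on which section is consulted.

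**Working it through.** **1. One event under the two wordings.** Three patients are treated at a level. One has a first DLT in Cycle 1 after an ibrutinib reduction that did not follow a DLT; the other two have none.

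- 7.31: counted DLTs 0/3. Under 16.222, three new patients go to the next higher level.
- 16.52 Note with 16.223: counted DLTs 1/3. Up to three more are treated at the same level, and escalation follows only if none of them has a DLT. That has probability (1 − p)³: 0.70³ = 0.343 at a true DLT rate p of 30%, and 0.60³ = 0.216 at 40%.

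This comparison needs no assumption about how often such an event occurs.

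**2. Reproducing the plan's table (16.227).** The cohort escalates after 0/3, or after 1/3 followed by 0/3:

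P(escalate) = (1 − p)³ + 3p(1 − p)² × (1 − p)³

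At p = 0.30: 0.343 + 0.151 = 0.494. At p = 0.40: 0.216 + 0.093 = 0.309. All five tabulated values reproduce, so the table describes a design in which every first-cycle DLT counts.

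**3. Effect if a share f of DLTs goes uncounted.** Replace p by p(1 − f). The documents give no value for f; the range below is an assumption.

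| True DLT rate | 16.227 | f = 0 | f = 5% | f = 10% | f = 20% |
|---|---|---|---|---|---|
| 10% | 0.91 | 0.906 | 0.914 | 0.922 | 0.937 |
| 20% | 0.71 | 0.709 | 0.730 | 0.752 | 0.793 |
| 30% | 0.49 | 0.494 | 0.525 | 0.557 | 0.622 |
| 40% | 0.31 | 0.309 | 0.343 | 0.378 | 0.454 |
| 50% | 0.17 | 0.172 | 0.202 | 0.234 | 0.309 |

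For f = 10% and p = 0.30 the counted rate is 0.27, and 0.73³ + 3(0.27)(0.73)⁵ = 0.389 + 0.168 = 0.557.

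**4. Effect on the selected MTD.** Assume true DLT rates of 5, 10, 20, 33 and 45% at levels −1, 1, 2, 3 and 4, and the same f at every level. Exact enumeration of the 16.22 rules, with six patients required at the MTD, gives the chance that the selected level has a true rate of at least 33%: 23.8% at f = 0, 27.1% at 5%, 30.7% at 10% and 38.8% at 20%. The curve is also an assumption.

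**5. Can the sequence arise?** 8.0 exempts the MTD-finding period and points to 7.31. 7.31 points back to Section 8 for modifications during Phase I, with no cycle limit. 8.51 and 15.19b lower ibrutinib itself, outside the adverse-event tables that the 8.2 heading covers. The documents do not rule the sequence out.

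**The case against.** The case against is substantial.

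- **Scope of Section 8.** The 8.2 heading places adverse-event reductions at Phase I Cycle 2 onward, and 7.31 can be read as inheriting that limit. On that reading f from this source is zero. This stands as a reason to expect few cases. It does not close the gap, because 7.31 has no cycle limit of its own and 8.51 and 15.19b lie outside the tables.
- **Few ibrutinib triggers.** Most triggers in 8.5 are themselves DLTs in Cycle 1, so the patient is already counted. First occurrences may restart at the same dose, and a toxicity delay of 14 days or more is itself a DLT. This also stands, and bears on frequency.
- **Dexamethasone.** A reader might infer that a dexamethasone reduction takes the patient off the first dose level, for example under the mood-alteration row of 8.4 ("Omit dexamethasone until symptoms resolve Restart with one dose level reduction"). The documents do not support this well. Levels −1 to 4 differ only in ibrutinib, patients aged 75 or older start on less dexamethasone within the same numbered level, and 12.4 treats the level as a category assigned at registration. The point should rest on ibrutinib reductions.
- **No true conflict.** The stopping sentence in 16.52 is tied to a dose level, and 7.31 points to 16.22, so the sections might be read as complementary. In that case the 7.31 condition governs and the DLT is simply uncounted. One could also read the first dose level as the assigned level, so that the DLT counts; but the preceding sentence in 7.31 uses dose level for the dose a patient restarts on. The text needs settling on any of these readings.
- **Safeguards.** DLTs go to the Study Chair (7.312), adverse events in all cycles are reviewed, enrolment stops for re-evaluation after a related Grade 4 or higher non-hematologic event in the first 3 patients, and the FDA reviews Phase I before Phase II. These reduce the risk but do not correct the count. The all-cycle review sets no counting rule, and the Grade 4 rule misses Grade 3 non-hematologic and all hematologic DLTs.

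**Conclusion.** The point holds as a gap in a counting rule for the Phase I primary endpoint. In the sequence described, 7.31 and the wording of 16.22 give different decisions for the same cohort, and the error from omission can only be toward escalation.

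A reader might infer that the MTD is set too high, or that the plan declares such a patient tolerant of the assigned level. The documents support neither. No passage states how the patient is scored; the 0/3 reading follows from 7.31 together with the absence of a replacement rule. The MTD can be biased upward, but the frequency is unknown and may be rare, so no actual bias can be computed. The rises of about 0.06 at a 30% true rate and 0.07 at 40% are illustrations that rest on the assumed 10% share. At a share of zero there is no effect.

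It is worth correcting because one sentence settles it.

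**What to change.** - In 7.31, replace the counting sentence with one stating that a patient's first DLT in Cycle 1 counts against the assigned dose level, whether it occurs at that level or after a reduction, and that later DLTs in the same patient are not counted again. This keeps the legitimate purpose of the present sentence.
- If the reduction was for a concomitant drug, a lower dose need not mean lower exposure. The sponsor may then prefer to declare the patient inevaluable and replace them. The patient must not be scored as free of DLT. That choice should be fixed in advance and applied to every patient so reduced, with or without a DLT, because replacing only those with a DLT would itself remove DLTs from the count.
- Cross-refer 16.22 and 16.52 to the new sentence, and align 13.5 and 16.226 if replacement is chosen.
- Reconcile 7.31 with 8.0 and 8.2 on whether reductions can occur in Phase I Cycle 1. Which clinical rule should apply is for the sponsor.

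The cost is one sentence and a few cross-references. It changes no dose or clinical rule and adds no procedures. In an affected cohort up to three more patients may be treated at the same level, or one patient replaced, and the MTD may come out one level lower.
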